4.6 Treatment Compliance

All study drugs will be administered to eligible subjects under the supervision of the investigators. The pharmacist will maintain records of preparation and dispensing, including the applicable lot numbers, patients' height, weight, and body surface, and total drug administered. Any discrepancy between the calculated dose and dose administered and the reason for the discrepancy must be recorded on the data capture records and in the source documents. Patients will also be given a log/diary on which to record rapamycin or ribavirin ingestion.

5.0 AGENT FORMULATION AND PROCUREMENT

5.1 Decitabine

Decitabine will be purchased from commercial sources.

5.1.1 Formulation Information

5.1.1.1 Product Identification

[figure not shown]
The generic name is decitabine or 5-aza-2'-deoxycytidine. The trade name in the United States is DACOGENTM for Injection.

5.1.1.2 Physical and Chemical Characteristics

Decitabine is a white to almost white finely crystalline powder, odorless substance, with a molecular formula of $C_8H_{12}N_4O_4$ and a molecular weight of 228.21 Daltons. The chemical structure is shown in Figure 1.

ULEU-13049 21 Version date: 09Aug2017

Figure 1: Chemical Structure of Decitabine

Decitabine is sparingly soluble in water (8 to 12 mg/mL), slightly soluble in ethanol and virtually insoluble in chloroform. Decitabine is an analog of 2'-deoxycytidine in which the #5-carbon atom of the pyrimidine ring has been replaced by a nitrogen atom. Decitabine appears in 2 configurations. The β -D-anomer is the pharmacologically active form; the α -D-anomer is almost inactive. The drug is most stable at pH 7 and when stored at low temperatures. $^{30\text{-}33}$

Dacogen[™] for Injection (decitabine) is supplied as a lyophilized preparation. Each 20-mL vial containing 50 mg decitabine should be stored at controlled room temperature per USP and is stable for at least 3 years if unopened.

Decitabine is a hypomethylating drug at lower doses and demonstrates direct cytotoxic properties at higher doses, therefore as with other potentially toxic compounds, caution should be exercised when handling and preparing decitabine. Decitabine should be aseptically reconstituted with 10 mL of Sterile Water for Injection (WFI); upon reconstitution, each mL contains approximately 5.0 mg of decitabine at pH 6.7 to 7.3. Immediately after reconstitution, the solution should be further diluted per recommended procedure with infusion fluids, such as 0.9% Sodium Chloride Injection, 5% Dextrose Injection, or Lactated Ringer's Injection to a final drug concentration of 0.1 to 1.0 mg/mL. Unless used within 15 minutes of reconstitution, the diluted solution must be prepared using cold infusion fluids (2°C to 8°C) and stored at 2°C to 8°C for a maximum of 7 hours prior to administration.

5.1.1.3 Other Pertinent Information

In stability studies, ³³ Dacogen for Injection maintains at least 95% of its initial potency for up to 60 minutes when a 50 mg vial is reconstituted

with 10 mL of either cold (2°C to 8°C) or room temperature water for injection (WFI). To assess potency, the decitabine was assayed by high-performance liquid chromatography (HPLC).

Reconstituted Dacogen for Injection (5mg/mL in WFI) was mixed with each of the approved diluents (0.9% sodium chloride injection, 5% dextrose injection or lactated Ringer's solution) and the stability was measured as above. The decitabine potency at diluted concentrations of 0.1 mg/mL and 1.0 mg/mL at either room temperature for 3 hours or refrigerated (2°C to 8°C) for 7 hours followed by 2 hours at room temperature remained \geq 90%. All admixtures of decitabine remained clear and colorless during storage at room temperature. Additionally, the pH of the solutions remained constant throughout the study.

Handling and Disposal

Procedures for proper handling and disposal of anticancer drugs should be applied. Several guidances on this subject have been published. There is no general agreement that all of the procedures recommended in the guidelines are necessary or appropriate.

5.1.1.4 The dosage of decitabine will be 20 mg/m2 given as an infusion on Days 1-10 of the first cycle and 1-5 of subsequent cycles.. Decitabine must be infused over 1 hour.

5.1.1.5 Adverse reactions

Table 1. Common Adverse Events Reported in a Phase III Trial Comparing decitabine to Supportive Care³³

	DACOGEN (n=83)	Supportive Care (n=81)
Neutropenia	75 (90%)	58 (72%)
Thrombocytopenia	74 (89%)	64 (79%)
Anemia NOS	68 (82%)	60 (74%)
Febrile neutropenia	24 (29%)	5 (6%)
Nausea	35 (42%)	13 (16%)
Constipation	29 (35%)	11 (14%)
Diarrhea NOS	28 (34%)	13 (16%)
Pyrexia	44 (53%)	23 (28%)
Hyperglycemia NOS	27 (33%)	16 (20%)
Cough	33 (40%)	25 (31%)
Petechiae	32 (39%)	13 (16%)

ULEU-13049 23 Version date: 09Aug2017

5.2 Rapamycin (from Rapamycin package insert)

Rapamycin can be obtained as Rapamune® from Wyeth-Ayerst Laboratories. It is approved for graft rejection prevention in kidney transplantation. It will be purchased from commercial sources for this protocol.

The oral solution must be protected from light and stored under refrigeration, 2 degrees Celsius to 8 degrees Celsius and it is stable for 24 months under these conditions. A slight haze may develop in refrigerated solutions, but the quality of the product is not affected. After opening, the solution should be used in 1 month. If necessary, it may be stored at temperatures up to 25 degrees Celsius for several days after opening (not longer than 30 days). Product may be stored in an amber syringe for a maximum of 24 hours (at room temperature or refrigerated). Discard syringe after use. Solution should be used immediately following dilution. The tablet should be stored at room temperature (20 degrees Celsius to 25 degrees Celsius) and protected from light.

Absorption: Rapid

Volume of distribution: 12L/Kg (+/- 7.52L/kg) Protein binding: 92%, primarily to albumin

Metabolism: Extensively hepatic via CYP3A3/4 and P-glycoprotien

Bioavailability: 14%

Half-life elimination: Mean: 62 hours

Time to peak: 1 - 3 hours

Excretion: Feces (91%); Urine (2.2%)

5.2.1. Adverse reactions

5.2.1.1. Systemic >10%:

Central nervous system: Insomnia, nervousness

Gastrointestinal: Increased appetite, indigestion, esophagitis

Dermatologic: Hirsutism

Endocrine/metabolic: Diabetes mellitus Neuromuscular & Skeletal: Arthralgia

Ocular: Cataracts Respiratory: Epistaxis

Metabolic: Increased triglycerides or cholesterol

<1% of case reports:

Seizures, mood swings, headache, delirium, hallucinations, euphoria, skin atrophy, bruising, hyperpigmentation, acne, amenorrhea, sodium and water retention, Cushing's syndrome, hyperglycemia, bone growth suppression, abdominal distention, ulcerative esophagitis, pancreatitis, muscle wasting, hypersensitivity reactions, pneumonitis in renal transplant patients, microangiopathic anemia in GVHD prophylaxis regimens only.

ULEU-13049 24 Version date: 09Aug2017

5.2.2. Drug Interactions

Cyclosporine may increase rapamycin concentrations due to inhibition of CYP3A4. In this protocol, active GVHD is an exclusion (see inclusion/exclusion section), so it is unlikely any patient would be on concurrent cyclosporine.

It is recommended that strong inducers and strong inhibitors of CYP3A4 and P-gp be avoided with rapamycin. Such agents include but are not limited to Rifampin, Rirabutin, Ketoconazole, Voriconazole, Itraconazole, Erythromycin, Telithromycin, and Clarithromycin.

Note: None of these are commonly used in AML patients except voriconazole, and it is recommended to avoid this. (See supportive care section of protocol, section 4.2). If any of these agents or other weaker inducers of CYP3A4 require usage, these can be utilized with caution especially since rapamycin levels will be monitored frequently in this protocol.

Grapefruit juice is to be avoided with rapamycin use.

5.3 Ribavirin (from Ribavirin package insert)

5.3.1 Description-- Ribavirin, (COEPEGUS) is a nucleoside analogue with antiviral activity. The chemical name of ribavirin is 1-β-D-ribofuranosyl-1*H*-1,2,4-triazole-3-carboxamide. It is available as a light pink to pink colored, flat, oval-shaped, film-coated tablet for oral administration. Each tablet contains 200 mg of ribavirin and the following inactive ingredients: pregelatinized starch, microcrystalline cellulose, sodium starch glycolate, cornstarch, and magnesium stearate. The coating of the tablet contains Chromatone-P® or Opadry® Pink (made by using hydroxypropyl methyl cellulose, talc, titanium dioxide, synthetic yellow iron oxide, and synthetic red iron oxide), ethyl cellulose (ECD-30), and triacetin.

5.3.2 CLINICAL PHARMACOLOGY

Mechanism of Action

• Ribavirin is an antiviral drug

Pharmacokinetics

- Multiple dose ribavirin pharmacokinetic data are available for HCV patients who received ribavirin in combination with peginterferon alfa-2a. Following administration of 1200 mg/day with food for 12 weeks mean±SD (n=39; body weight greater than 75 kg) AUC0-12hr was 25,361±7110 ng·hr/mL and Cmax was 2748±818 ng/mL. The average time to reach Cmax was 2 hours.
- The terminal half-life of ribavirin following administration of a single oral dose of is about 120 to 170 hours. The total apparent clearance following administration of a single oral dose of is about 26 L/h. There is extensive accumulation of

ULEU-13049 25 Version date: 09Aug2017

ribavirin after multiple dosing (twice daily) such that the Cmax at steady state was four-fold higher than that of a single dose.

Effect of Food on Absorption of Ribavirin

- Bioavailability of a single oral dose of ribavirin was increased by coadministration with a high-fat meal.
- Elimination and Metabolism
- The contribution of renal and hepatic pathways to ribavirin elimination after administration of is not known. In vitro studies indicate that ribavirin is not a substrate of CYP450 enzymes.
- Renal Impairment
- A clinical trial evaluated 50 subjects with either moderate (creatinine clearance 30 to 50 mL/min) or severe (creatinine clearance less than 30 mL/min) renal impairment or end stage renal disease (ESRD) requiring chronic hemodialysis (HD). The apparent clearance of ribavirin was reduced in subjects with creatinine clearance less than or equal to 50 mL/min, including subjects with ESRD on HD, exhibiting approximately 30% of the value found in subjects with normal renal function. Pharmacokinetic modeling and simulation indicates that a dose of 200 mg daily in patients with severe renal impairment and a dose of 200 mg daily alternating with 400 mg the following day in patients with moderate renal impairment will provide plasma ribavirin exposures similar to that observed in patients with normal renal function receiving the standard 1000/1200 mg daily dose. These doses have not been studied in patients.

5.3.3 Adverse Effects

6.3.3.1 Ribavirin therapy should not be started unless a report of a negative pregnancy test has been obtained immediately prior to planned initiation of therapy. Extreme care must be taken to avoid pregnancy in female patients and in female partners of male patients. Patients should be instructed to use at least two forms of effective contraception during treatment and for 6 months after treatment has been stopped. Pregnancy testing should occur monthly during therapy and for 6 months after therapy has stopped.

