6.0 STUDY CALENDAR (Appendix 5)

Baseline evaluations are to be conducted within 1 week prior to the start of the protocol unless otherwise specified.

Before beginning the treatment protocol, each patient will have the following performed:

- Complete history and physical exam including: Demographics, past medical and surgical history, medications, allergies, vital signs, height, weight, systemic exam including neurological exam
- EKG and Chest x-ray
- Bone marrow aspirate/biopsy, cytogenetics, molecular diagnostic studies to assess for the
 presence of FLT-3 or NPM-1 mutations and flow cytometry within 2 weeks of treatment.
 If these studies were performed elsewhere, an aspirate only will be performed to obtain
 material to perform the baseline correlative studies that are part of the protocol. (See
 section 8).
- CBC with differential, platelet count
- Chemistry including complete liver function tests, BUN/Cr, LDH and other electrolytes
- Uric acid level
- Urine analysis and urine pregnancy test for female patients of childbearing potential
- DIC panel
- Peripheral blood for correlative studies (See section 8 and Appendix 5)

After the beginning of each cycle, each patient will have the following tests performed at the noted time points:

- CBC with differential and platelets twice per week
- Chemistry including liver function tests, BUN/Cr and other electrolytes twice weekly
- Triglycerides and cholesterol on Day 1 of each cycle for those on Arm A (rapamycin) only
- Abbreviated physical examination and assessment of performance status
- A bone marrow aspirate only will be performed on Day 10 or 11 of therapy after completion of the decitabine and before initiation of rapamycin or ribavirin in CYCLE 1 ONLY for correlative studies including the phosphorylation status of mTOR effectors and stem cell frequency.
- A trough rapamycin level (arm A only) will be drawn on day 14 and 21 of each cycle. A level will also be drawn on Day 1 of Cycle 2 to assure a subtherapeutic level when decitabine is started in subsequent cycles only if the level on Day 21 was elevated.
- A bone marrow aspirate and biopsy will be performed after the completion of cylces 1, 3, and at the end of the study. This may occur on Days 22 through 26 of the cycle.
- A marrow aspirate and biopsy will also be performed at time of suspected disease progression and at study completion or at any other time the treating physician deems important for disease status determination

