APPENDIX 5 (ARM B) Decitabine and Ribavirin

Tests	Pre										I	Days												
		1	2	3	4	5	6	7	8	9	10	11	12	13	14	15	16	17	18	19	20- 22	22-26	28	EOS
Decitabine		X	X	X	X	X	• X9	X9	X9	X ⁹	X ⁹													
Ribavirin ⁸		X ¹⁰	X 10	X ¹⁰	X	X	X	X	Х	X	X	X	X	X										
History & Physical	X	X																						
CBC w/diff & plts	X	X						X ³																
Chemistries	X	X8						X ³																
LDH	X					X		X ³																
Urate	X	X						X ⁴																
Bone marrow	X										X^1												X1	X ¹
Flow Cytometry	X																					X		
Cytogenetic Studies	X																					X		
DIC Panel	X																							
Molecular Studies ¹²	X																							
Bone marrow for Correlative Studies	X ⁵ 40cc										X ⁵ 40cc											X ⁵ 40cc		
Blood for correlative studies	X ⁷ 10cc										X ⁷ 10cc											X ⁷ 10cc		
EKG/CXR	X																							
U/A, PT, PTT, Pregnancy	X																							
Chimerism	X ²																						X ²	
Evaluation of Response																							X ⁶	X ⁶
Long Term Follow Up																								X ¹¹

 Aspirate only in cycle 1 on day 10-11 and biopsy and aspirate at days 22-26 of cycles 1 and 3 for disease assessment and at end of study. Marrows may also be performed when clinically indicated at other times for disease assessment. Substitution of peripheral blood may be acceptable if aspirate/marrow cannot be obtained.

Complion Document ID: 1248945

- 2. In those patients who have had an allogeneic transplant by chromosome (sex mismatched transplants) or by PCR assay. This can be done on either blood or marrow at physicians' choice.
- 3. Twice per week or as clinically indicated
- 4. As indicated clinically
- 5. 40 cc aspirate in green top (heparinized) tubes; if marrow is a dry tap, substitute 40 cc blood total
- 6. Cycles 1 and 3 only and at end of study or study discontinuation.
- 7. 10cc in green top tube.

- 8. After cycle 1, ribavirin will begin on day 1 and will be given continuously without interruption unless for toxicity.
- 9. Decitabine is given days 1-10 during cycle 1. In subsequent cycles, decitabine is given days 1-5.
- 10. Ribavirin is given continuously starting on day 1 of Cycle 2.
- 11. Every 6 months for up to 2 years after date of last treatment
- 12. Molecular studies completed previously are acceptable if results are in the medical record.

All time points refer to all cycles except where noted. The window for protocol visits and assessments is +/- 3 days.

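### The pregnancy tests that Section 5.3.3 asks for around ribavirin are not carried into Section 6.0 or the Arm B calendar, which schedule a single pre-study test

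*Combined protocol and SAP*

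**What the plan says.** Section 5.3.3 gives three testing instructions for ribavirin. On starting the drug: "Ribavirin therapy should not be started unless a report of a negative pregnancy test has been obtained immediately prior to planned initiation of therapy". On later testing: "Pregnancy testing should occur monthly during therapy and for 6 months after therapy has stopped". It also covers contraception: "Patients should be instructed to use at least two forms of effective contraception during treatment and for 6 months after treatment has been stopped". Section 5.3 is headed as coming from the package insert.

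Section 6.0 lists the test once: "Urine analysis and urine pregnancy test for female patients of childbearing potential". The list that holds it opens with "Before beginning the treatment protocol, each patient will have the following performed", and the timing rule is "Baseline evaluations are to be conducted within 1 week prior to the start of the protocol unless otherwise specified". The separate list of tests for each cycle has no pregnancy test.

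In the Arm B calendar, the row "U/A, PT, PTT, Pregnancy" is marked only in the pre-study column. The treatment days and the end-of-study column are blank for that row, and no footnote is attached to it.

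Section 4.1.1 starts ribavirin on day 11 of cycle 1 and gives it continuously from day 1 of cycle 2. Section 4.1.1.1 sets 28-day cycles (extendable to 30 days), a maximum of six cycles, and a survival check at six-month intervals after treatment.

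**The concern.** Staff usually work from the study calendar. A site that follows Section 6.0 and the Arm B calendar exactly would start ribavirin on a test done before decitabine began, and would do no further test during or after ribavirin. The same protocol asks for all of these tests and stresses great care to avoid pregnancy with this drug. The two sets of instructions do not agree, and nothing in the protocol text explains the difference.

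What is at stake is the safety of a small group: women of childbearing potential in Arm B. Response, dose-limiting toxicity and the stopping rules are not involved.

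**Working it through.** The plan gives no figure of its own to reproduce. The check is schedule arithmetic.

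**Age of the scheduled test at the first ribavirin dose**

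Inputs: first ribavirin dose on day 11 (Section 4.1.1); baseline tests up to 7 days before the start (Section 6.0); a window of 3 days either way for visits and assessments (note under the Arm B calendar).

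- Test on day 1, before treatment: 11 − 1 = 10 days.
- Test 7 days before day 1: 10 + 7 = 17 days.
- With the 3-day window applied in the more favourable and the less favourable direction: 10 − 3 = 7 and 17 + 3 = 20 days.

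The range is 10 to 17 days nominally and about 7 to 20 days with the window. The lower end is generous: moving the first dose 3 days earlier, to day 8, would place it within the ten decitabine days. No value in either range fits a test required immediately before the drug starts.

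**Number of tests**

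For N cycles, take one test before day 11 of cycle 1, one on day 1 of each later cycle (28 days, close to monthly), and six monthly tests afterwards:

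1 + (N − 1) + 6 = N + 6

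| Cycles | Called for by Section 5.3.3 | Scheduled |
|---|---|---|
| 1 | 7 | 1 |
| 3 | 9 | 1 |
| 6 (maximum) | 12 | 1 |

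The last row assumes all six cycles and complete follow-up, so it is a ceiling.

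**Could the calendar be read as repeating the test?**

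A general note under the calendar applies time points to every cycle unless stated otherwise. Section 6.0, however, places this test before treatment begins and leaves it out of the per-cycle list. Even if the pre-study column were repeated each cycle, the test before the first ribavirin dose (1) and the tests after therapy (6) would still be missing: 1 + 6 = 7, whatever the number of cycles.

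**Who is affected**

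- Only patients with M4 or M5 disease receive ribavirin (Section 4.1.1).
- Section 11.0 allows at most 6 patients per dose level. Three levels on either path (1, 2, 3 or 1, −1, −2) give 3 × 6 = 18 patients of both sexes. The size of the later phase II expansion is not stated.
- Newly diagnosed patients must be over 65 (3.1.6), but the general age limit is 18 (3.1.1), so younger relapsed or refractory women can enter.
- In the earlier phase I study of decitabine and rapamycin in relapsed or refractory disease (Section 2.6), the median age was 63, range 46 to 78.

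The documents do not give the number of women of childbearing potential. These figures suggest that it is very small and may be zero.

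**The case against.** The strongest reply is that the requirement is already in force. Section 5.3.3 is current protocol text, and neither Section 6.0 nor the calendar cancels it. Pregnant patients are excluded at entry (3.2.6), and two forms of contraception are asked for during treatment and for six months after. On this view the fault is a missing cross-reference. Much of this stands. A reader might infer that the protocol leaves women on ribavirin without pregnancy precautions; the documents do not support that. What remains is that the schedule staff work from omits tests the protocol asks for. The exclusion applies at entry, and contraception is a separate instruction from testing.

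A second reply is that Section 5.3 is label text worded as advice. That is true of its origin and tone, but it sits in the protocol, and the text available for review does not waive it. Consent pages were not available, so nothing is claimed about them.

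A third is that the affected group is tiny. This is accepted and limits the weight of the point.

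A reader might also infer that contact after treatment is limited to survival checks. That is too strong. Section 6.0 and the calendar include an end-of-study evaluation, although Section 4.1.1.1 makes the marrow at withdrawal optional. That evaluation can carry one test but cannot cover six months.

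**Conclusion.** The point holds as an internal inconsistency with a safety consequence, and it should be corrected. Its size is one scheduled test, nominally 10 to 17 days (about 7 to 20 with the window) before the first ribavirin dose, where Section 5.3.3 calls for 7 to 12 tests depending on the number of cycles. This rests on reading Section 5.3.3 as applying to the trial, on counting one test per cycle as monthly, and, for the counts, on complete follow-up.

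It does not support a claim that many patients are at risk, or that the design, endpoints or analysis are affected. The gap at the first ribavirin dose matters most, because it can be closed at a visit that already exists.

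**What to change.** For women of childbearing potential in Arm B, add to Section 6.0 and to the Arm B calendar:

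- (a) A urine pregnancy test with a negative result at the cycle 1 visit that already exists for the marrow sample ("A bone marrow aspirate only will be performed on Day 10 or 11 of therapy after completion of the decitabine"), before the first ribavirin dose. State that the 3-day window may not move this test past that dose.
- (b) A urine test on day 1 of each later cycle, when patients already attend for decitabine.
- (c) A test at the end-of-study visit, with a footnote pointing to the six months of testing in Section 5.3.3, done locally or by home urine test where there is no visit.

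This needs a written amendment under Section 14.0. On treatment the cost is one urine test per cycle at existing visits. After treatment there is a modest burden on ill patients, some of whom will not complete it, but Section 5.3.3 already asks for that testing. If the sponsor considers the follow-up impracticable, it should amend Section 5.3.3 and give its reason; (a) and (b) should be added in any case.
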